#### Intra-operative stage to collect objective measurements

Objective measurements, for example Auto-NRT and impedance telemetry are commonly used test procedures to test the implant function intra- and post-operatively. These measurements utilise the capability of the internal implant to run telemetry tests when commanded by the sound processor. Currently these tests are run either via a computer with Custom Sound **software or with a remote control or App on a mobile device handled by the professional**.

These objective data can be used in fitting and can eventually help the clinician with predicting outcomes, increase performance and optimise the clinicians' efficiency in diagnostics.

In this investigation, only CE approved devices will be used for this intra-operative testing in accordance with the approved indication(s) and terms of the market authorization. Post-operatively, these subjects might be recruited following the procedures as described for the group 1 subjects.

Comparison of programming, diagnostic and/or (re)habilitation methods is typically conducted using repeated-measures design, in which each subject is acting as his/her own control, which accommodates the heterogeneity across the population. The baseline condition will be compared to one or more of the investigational conditions.

As mentioned in section 4.1, this umbrella investigation will be conducted in different sub-studies to assess the incremental change of the software functionality and/or to assess the concept of a new diagnostic, fitting or (re)habilitation method. Each of the sub-studies will be looking at a particular approach to address the objectives of the overall umbrella investigation AI5763.

Since different methods will be tested, subjects may be recruited for multiple sub-studies, during the full duration of the umbrella investigation. Each subject can only participate in one sub-study at a time.

CI recipients from the age of 10 months upwards can participate in the study, as long as they meet the inclusion and exclusion criteria as described in section 7.2. Children are included in the study as they are a specific group of CI users, requiring adapted fitting, diagnostic and (re)habilitation methods compared to adult CI users. The procedure for recruiting subjects is further described in section 7.2.

Where possible, each sub-study will be blinded (i.e. information is concealed from the recipient) or double-blinded (i.e. information is concealed from the recipient and the investigator) and randomized (i.e. the order of testing).

Given that the sub-studies are feasibility studies, there is no need to statistically power the study. However, where possible sample size calculation will be made to enable assessment of non-inferiority or superiority. This is described in section 9.

### 7.2 Subjects

Written, informed consent must be obtained from the subject or subject's legally authorized representative before any study procedures are initiated.

Eligibility of subjects shall be supported by medical, demographics and audiological information that confirm the subject inclusion as stated in section 7.2.1.

Up to 160 adult and paediatric CI recipients older than 10 months can participate into the umbrella study. Each sub-study will specify their own subject population and indications for which the IMD is intended, within the population and indications of the umbrella investigations. Paediatric subjects will be enrolled in Belgium only

#### 7.2.1 Inclusion Criteria

Subjects must meet all the inclusion criteria described below to be eligible for this clinical investigation.

 Group 1 subjects: Users of a CE approved Nucleus cochlear implant, resulting in open set speech understanding or

Group 2 subjects: Subjects assessed by their CI clinic to be suitable for implantation with a commercially available CE approved Nucleus cochlear implant.

 Paediatrics: Older than 10 months and <18 years when entering the study (Belgium only) or

Adults: ≥18 years when entering the study (Belgium and Australia)

- Subject/legally designated representative is fluent speaker in the language used for assessments.
- Willing and able to provide written informed consent (for paediatric populations this criterion applies to the parent/legally designated representative).

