## 2 CLINICAL INVESTIGATION SYNOPSIS

Investigation title	A feasibility, prospective, repeated-measures investigation to investigate innovations in clinical care in adult and paediatric recipients implanted with CE approved Nucleus cochlear implants: an umbrella investigation.	
Short title	Clinical Care	
Investigation number	AI5763	
Name of investigational medical device(s)	New/improved fitting, diagnostic and (re)habilitation software and/or research tools/methods.	
Intended use of investigational medical device(s)	Exclusively used for feasibility study only. Pre-market.	
Name and description of comparator device/product(s)	Commercially available fitting, diagnostic and (re)habilitation software and/or tool/method where available.	
Estimated recruitment period	Up to 4 years and 10 months (October 2024).	
Expected duration per subject	Up to 5 years.	
Number of subjects planned	Maximum 160 subjects enrolled in a collection of feasibility sub-studies. Belgium: Adults and children Australia: Adults only	
Number of investigational sites planned	5	
Inclusion criteria	• Group 1 subjects: Users of a CE approved Nucleus cochlear implant, resulting in open set speech understanding or Group 2 subjects: Subjects assessed by their CI clinic to be suitable for implantation with a commercially available CE approved Nucleus	
	
 
Paediatrics: Older than 10 months and <18 years when entering the study (Belgium only) or
 
	
	
 
Adults: ≥18 years when entering the study (Belgium and Australia).
 
Subject/legally designated representative is fluent speaker in the language used for assessments.
 
	
	
 
Willing and able to provide written informed consent (for paediatric populations this criterion applies to the parent/legally designated representative).
 
	
Exclusion criteria	
 
Unable or unwilling to comply with the requirements of the clinical investigation as determined by the investigator.
 
	
	
 
Additional health factors, known to the investigator, that would prevent or restrict participation in the audiological evaluations.
 
	
	
 
Investigator site personnel directly affiliated with this study and/or their immediate families; immediate family is defined as a spouse, parent, child, or sibling.
 
	

Clinical Investigation Plan: AI5763

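### Does the open-set speech condition for Group 1 defeat the plan's provision for cochlear implant recipients from 10 months of age?

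*Combined protocol and SAP*

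**What the plan says.** Section 7.2.1 opens with "Subjects must meet all the inclusion criteria described below to be eligible for this clinical investigation". Its first criterion has two branches joined by 'or'. The first branch, Group 1, reads "Users of a CE approved Nucleus cochlear implant, resulting in open set speech understanding", and the synopsis repeats it. The second branch, Group 2, reads "Subjects assessed by their CI clinic to be suitable for implantation with a commercially available CE approved Nucleus cochlear implant" and has no speech condition. The paediatric age range, older than 10 months and under 18 years (Belgium only), applies to both branches.

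On children, section 7.1.1 says "CI recipients from the age of 10 months upwards can participate in the study, as long as they meet the inclusion and exclusion criteria", and gives as the reason that children are a distinct user group "requiring adapted fitting, diagnostic and (re)habilitation methods compared to adult CI users". Section 7.2 says "Up to 160 adult and paediatric CI recipients older than 10 months can participate into the umbrella study" and lets each sub-study define its own population, but only "within the population and indications of the umbrella investigations". Section 7.2.3 confines paediatric recruitment to sub-studies that cannot do without children, and section 7.2.4 says children may be involved depending on what is tested.

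Section 7.1 describes Group 1 simply as people who already have a Nucleus implant and does not mention open-set speech. It describes Group 2 as people booked for implantation, who may afterwards take part under the Group 1 procedures.

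**The concern.** Many very young implanted children can be expected not to have open-set speech yet. On a strict reading of 7.2.1 they cannot enter as Group 1, whatever the sub-study is testing. The rule also covers diagnostic, training and usability sub-studies, for which the word score in 9.2.1 is not the stated endpoint. Table 1, the example post-operative test battery, lists language development tests for young children, so the authors evidently had such children in mind after surgery.

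Nor can the restriction be lifted lower down. Section 7.2 keeps sub-studies inside the umbrella population, and section 13 allows deviations only in an emergency. If a sub-study needed young children who were implanted before entry, the site would face ineligible referrals, screen failures or eligibility deviations, and the results would not cover the group that 7.1.1 says needs adapted methods. Because 7.1 omits the speech condition that 7.2.1 imposes, two sites could also answer the eligibility question differently.

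**Working it through.** No sample size or power figure is involved: 160 is a ceiling, and section 7.2.3 states that there is no power calculation at umbrella level. The check is one of eligibility logic.

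**Step 1. The criterion as logic.** From 7.2.1:

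Eligible = [(implant user AND open-set speech) OR (assessed as suitable for implantation)] AND (age and country rule) AND (remaining criteria).

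**Step 2. Apply it to the possible cases,** assuming the other criteria are met.

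| Person | Group 1 | Group 2 | Can enter |
|---|---|---|---|
| Implanted, with open-set speech, older than 10 months | yes | not needed | yes |
| Child older than 10 months, not implanted, implant candidate | no | yes | yes |
| Implanted child, no open-set speech, assessed for a second implant | no | yes on the wording of 7.2.1 | probably |
| Implanted child, no open-set speech, not a candidate for another implant | no | no | no |

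Only the last row is closed. The lower age limit can still be reached through the second row.

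**Step 3. How firm is the stated intent?** Five sections provide for participants from 10 months.

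- 7.1: states that such subjects will be included.
- 7.1.1: they can participate, provided that they meet the criteria.
- 7.2: they can participate.
- 7.2.3: they could be recruited, if a sub-study cannot do without them.
- 7.2.4: they might be involved.

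One of the five is firm and 5 − 1 = 4 are permissive. Group 2 satisfies the firm one.

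Two of the five, 7.1.1 and 7.2, speak of recipients, which might suggest children who already have an implant. But 7.2 uses the word for all of the up to 160 subjects, including Group 2 subjects, who need not have an implant at entry. It cannot carry that inference.

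**Step 4. Is there a reason for the rule?** The only umbrella endpoint is the monosyllabic word score in quiet for fitting methods (9.2.1). The version 6.0 entry in section 25 says that most of the research will evaluate fitting methods and that this score is to be the consistent measure in all such sub-studies. A subject who cannot understand words without prompts would score at or near the floor under both fittings and add little to that comparison. The rule fits the main work, although it is broader than that work strictly needs.

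**Step 5. What happens to the analysis?** Section 9.1 analyses each sub-study separately, and sections 7.1.1 and 7.3 use repeated measures with each subject as own control. An entry rule applied before any comparison restricts the population to which results apply. It does not bias the within-subject contrast, and no pooled umbrella analysis exists for it to distort.

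**Step 6. How many children?** The open-set rule stands in 2 places (7.2.1 and the synopsis) with 0 exceptions. The documents give no planned number of children and no age at which open-set speech is reached, and no sub-study plan is among them. The number affected cannot be derived and may be zero.

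**Step 7. What would a change achieve?** There are two routes.

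- *Require open-set speech only where the word score is primary.* This would lift the rule for adults too, although the gap concerns some children. Applied evenly, it would place a new condition on Group 2 subjects who continue after surgery. Admitting children without open-set speech to fitting work would also need a different primary endpoint there, against the version 6.0 rationale. It widens entry for young children, so it would probably be a substantial amendment needing written ethics approval (section 16) and the agreement of the Principal Investigators and the Sponsor (section 18). The synopsis gives October 2024 beside the recruitment period, so the benefit depends on the time left.
- *State that already implanted children without open-set speech are not included.* This records what 7.2.1 already implies. It changes no subject's eligibility and no result.

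**The case for a change.** The strongest argument for acting is that Group 2 is only a partial route. It is built around testing in the operating theatre, and later participation is only a possibility. The plan does not say whether the open-set condition applies once such a child moves to post-operative work. If it does, the gap is wider. If it does not, two children with the same implant and the same speech ability are treated differently only because one was enrolled before surgery. Section 7.1 also describes Group 1 more broadly than 7.2.1.

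Part of this stands. The two descriptions of Group 1 differ, and the position of continuing Group 2 subjects is not spelled out. Neither point leaves the study without a workable rule. Section 7.2.1 is the operative eligibility text, and it requires every criterion to be met; the summary in 7.1 does not override it. For continuing Group 2 subjects, 7.1 refers to the procedures of Group 1 and not to its entry criterion, so the natural reading is that someone admitted as Group 2 stays admitted. Each sub-study must in any case define its own population under 7.2 and may be narrower than the umbrella, so a sub-study plan can settle the matter for its own subjects.

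The fear of screen failures is also limited. Under 7.2.5 a screen failure is a subject who has already signed consent, and a child known to lack open-set speech need not be enrolled at all.

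**Conclusion.** The observation is right but small. The open-set condition has no exception by age or sub-study, a sub-study cannot relax it, and it excludes children implanted before entry who lack open-set speech and are not candidates for another implant. It narrows the provision for young recipients without defeating it: candidates older than 10 months can enter as Group 2, paediatric recruitment is optional, and 7.1.1 subjects the age statement to the criteria.

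This is a fair trade-off between breadth of entry and a common, usable outcome measure, with a wording gap that sub-study plans are already required to fill. No analysis or result changes. The conclusion assumes that 7.2.1 governs over the summary in 7.1, and that no sub-study depends on the excluded children; the documents neither show nor rule out such a sub-study. If one were proposed, its own submission would be the place to argue for wider entry, with a discussion of risk for those children. On the documents available, no change to the umbrella plan is warranted.

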#### 7.2.2 Exclusion Criteria

Subjects who meet any of the exclusion criteria described below will not be eligible for this clinical investigation.

- Unable or unwilling to comply with the requirements of the clinical investigation as determined by the investigator.
- Additional health factors, known to the investigator, that would prevent or restrict participation in the audiological evaluations.
- Investigator site personnel directly affiliated with this study and/or their immediate families; immediate family is defined as a spouse, parent, child, or sibling.
- Cochlear employees or employees of Contract Research Organizations or contractors engaged by Cochlear for the purposes of this investigation.
- Currently participating, or participated within the last 30 days, in another interventional clinical investigation/trial involving an investigational drug or device.

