## 7 DESIGN OF THE CLINICAL INVESTIGATION

## 7.1 General

This is a feasibility, prospective, with sequential enrolment, multicenter, clinical investigation in adults and paediatrics with a CE approved Nucleus cochlear implant.

Subjects older than 10 months will be included. Subjects will be screened and up to 160 eligible subjects will be recruited in the umbrella investigation.

Two separate groups of subjects will be recruited:

- Group 1 will include subjects who are already implanted with a Nucleus cochlear implant. A clinical setting can consist of therapeutic elements (fitting, diagnostic or rehabilitation) and evaluations. Subjects will be assessed with the commercially available Nucleus sound processor. Acute testing will be done where possible. Take home use will be applied when learning effects may play a significant role and to evaluate the acceptance of the different fitting, diagnostic and (re)habilitation methods in as many listening environments as possible. The subject might be asked to complete questionnaires, to perform at-home tests etc. during this take home use and/or at the clinical visits. The time for a clinical visit will be limited to a maximum of 4 hours. The time in between clinical visits will vary with typical spacing of between 0 (acute) to 4 weeks.
- Group 2 will include subjects who are scheduled to be implanted with a commercially available Nucleus cochlear implant. The diagnostic testing will be conducted in the operating theatre during the cochlear implant surgery. Only CE approved devices will be used for this intraoperative testing in accordance with the approved indication(s) and terms of the market authorization. Post-operatively, these subjects might be recruited following the procedures as described for the group 1 subjects.

Figure 5 illustrates the subject enrolment scenarios for group 1 and group 2 subjects.

Subjects will attend scheduled study visits over a period up to 5 years in different sub-studies as described in the sub-study documentation.

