#### 7.2.5 Recruitment and Study Duration

The following subject status definitions apply:

Enrolled: A subject that has a signed Informed Consent form for the study.

Screen Fail: an enrolled subject that has been determined to not meet one or more eligibility criteria.

Participated: Subjects who have met all eligibility criteria and started on protocol defined procedures.

Withdrawn: An Enrolled subject who withdrew or was withdrawn by the Investigator or Sponsor before the expected End of Study visit. Withdrawn subjects may still continue in safety follow up until their scheduled End of Study visit, for reasons described in section 7.2.6.

The recruitment period for the clinical investigation is estimated to be 4 years and 10 months from the time of first subject consent to recruitment of the last subject. No new subjects will be recruited in the last 2 months of the study.

Each participant can participate in several sub-studies (one at a time).

Clinical Investigation completion is last subject last visit. In the event of ongoing Serious Adverse Events (SAEs)/Serious Adverse Device Effects (SADEs) at the time of this last visit, the clinical investigation completion will be extended for a further 30 days, or until resolution or stabilization of the event, whichever comes first. Any variations to these requirements will be documented in each substudy documentation (for example, variations to account for in-booth only or take-home use).

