#### Australia:

External site: HEARnet (in collaboration with Royal Victorian Eye and Ear Hospital, East Melbourne)

Internal (Cochlear) site: Cochlear Ltd. Melbourne.

The principal investigators of the external sites are responsible for subject recruitment, obtaining Informed Consent, assessment of inclusion and exclusion criteria and assessment of hearing and medical history related to this umbrella Clinical Investigation Plan. Subjects may then be referred to the sponsor principal investigator of internal (Cochlear) sites, who will conduct the remaining study procedures as described in the umbrella and sub-study Clinical Investigation Plan. Section 10 describes the Informed Consent process.

The following scenarios for sub-studies are distinguished:

- The sponsor principal investigator or study staff of internal (Cochlear) sites will conduct study procedures at the facilities of internal (Cochlear) sites. The conduct of the study procedures is the responsibility of the sponsor principal investigator.
- The sponsor principal investigator or study staff of internal (Cochlear) sites will conduct study procedures at the facilities of the site of the external principal investigator. The conduct of these study procedures remains the responsibility of the sponsor principal investigator of internal (Cochlear) sites.
- The external principal investigator or study staff of external site(s) will conduct study procedures at the facilities of the site of the external principal investigator. The conduct of the study procedures is the responsibility of the external principal investigator.
- The external principal investigator or study staff of the external principal investigator will conduct study procedures at the facilities of internal (Cochlear) sites. The conduct of these study procedures remains the responsibility of the external principal investigator.

For all scenarios, the coordinating investigator of the sub-study is the coordinating investigator of the umbrella investigation. Study staff (e.g. technical expert) of the external site(s) of the umbrella study may conduct study procedures for which the sponsor principal investigator of a sub-study is responsible, only in case the study staff have the qualification and competence to conduct these study procedures. The conduct of these study procedures is the responsibility of the sponsor principal investigator.

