#### 7.4.1 Concomitant Medication and Therapies

In case of concomitant medication, this is administered as part of the safety Clinical Report Forms.

Possible interactions with concomitant medications are not anticipated in this clinical investigation. Information on baseline concomitant medication (all medications related to hearing health, balance or known ototoxic) will be collected during enrollment for each sub-study. In the event of AE's and ADE's, any medications taken in relation to these events will also be collected.

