## 14 DATA MANAGEMENT

On umbrella study level information about eligibility, demographics, medical, hearing and device history, protocol deviations and completion of study will be obtained. On sub-study level also adverse event, device deficiency and sub-study specific information will be captured.

The CRF will capture the datapoints necessary to determine the subject status according to the criteria described in section 7.2.5.

Source data will be captured in clinic notes, paper-based source data worksheets, questionnaires or printed directly from testing software. Data such as clinical performance data, questionnaires etc. can be entered directly into the eCRF which shall be considered source data for these items. If electronic medical records do not permit read only access for monitoring purposes, a certified printout must be provided.

The system used for data collection will be specified at the sub-study level, including the use of electronic data capture (EDC) on eCRFs.

In addition, de-identified electronically generated data will be collected from clinical fitting software, objectives measures software, imaging (such as CT), videography, diagnostic tools etc. The unamended data file shall be regarded as the source.

In case the full eCRF option is not utilized, data collection for demographics, device exposure, medical history, adverse events, device deficiencies, concomitant medications, protocol deviations and completion will be performed using electronic data capture (EDC) on electronic Case Report Forms (Safety eCRF), to support safety analysis and reporting. All other data will be collected from clinical fitting software, objectives measures software, imaging, videography, clinical performance data etc. or captured into paper Case Report Forms and entered in a suitable database or directly into the study report after review by the study monitor. In case specific procedures are used for data management such as data collection and review, this will be specified in the sub-study documentation. Site personnel will be trained on the completion of the CRFs. Unamended data files shall be regarded as the source.

Site personnel will be trained on the completion of the eCRF prior to obtaining access to the system and will have their own Login/Password. Access to clinical study information will be based on an individual's role and responsibilities.

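### Does the umbrella plan let subjects enter later sub-studies of AI5763 without a fresh eligibility check?

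*Combined protocol and SAP*

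**What the plan says.** Section 7.2.2 sets its criteria at the level of the whole investigation: "Subjects who meet any of the exclusion criteria described below will not be eligible for this clinical investigation". One of them excludes a person "Currently participating, or participated within the last 30 days, in another interventional clinical investigation/trial involving an investigational drug or device". The bullet gives no date from which the 30 days are counted.

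Section 7.3 makes the external principal investigators responsible for "assessment of inclusion and exclusion criteria and assessment of hearing and medical history related to this umbrella Clinical Investigation Plan", after which subjects may be referred to an internal site. Section 14 divides the data by level. For the umbrella: "On umbrella study level information about eligibility, demographics, medical, hearing and device history, protocol deviations and completion of study will be obtained". For the sub-studies: "On sub-study level also adverse event, device deficiency and sub-study specific information will be captured". Section 7.2.5 defines participated status as "Subjects who have met all eligibility criteria and started on protocol defined procedures".

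Participation can be long and serial. Section 7.1 states: "Subjects will attend scheduled study visits over a period up to 5 years in different sub-studies". Sections 4.1 and 7.1.1 limit a subject to one sub-study at a time.

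Section 7.2.1 gives two alternative ways in. Group 1 are implant users with open-set speech understanding. Group 2 are candidates judged suitable for implantation, with no speech criterion. Sections 7.1, 7.1.1 and 7.3 allow Group 2 subjects to be recruited after surgery under the Group 1 procedures. The primary endpoint in section 9.2.1 is the monosyllabic word score in quiet.

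**The concern.** Eligibility is assessed against the umbrella plan and listed among the umbrella data. Where the plan wants something repeated it says so: section 7.4.1 has baseline medication that "will be collected during enrollment for each sub-study". Nothing comparable is said of eligibility. If the criteria were answered once only, two weaknesses would follow.

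- **The 30-day exclusion.** Suppose two people each finish an outside device trial 10 days before the same sub-study opens. The one joining AI5763 that day is excluded. The one who joined a year earlier is admitted. The one-at-a-time limit does not help, because it concerns sub-studies of AI5763 and not outside trials.
- **Open-set speech.** A Group 2 subject could reach a fitting sub-study without ever being shown to have measurable open-set understanding. A subject who scores at floor with both maps contributes a difference near zero whatever the new method does. That pulls the estimate towards no difference, which helps the new method if non-inferiority is assessed, a possibility that section 7.1.1 leaves open.

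**Working it through.** The plan has no figure to reproduce. It gives no margin, SD, alpha or sample size at umbrella level, and 160 is a recruitment ceiling without a calculation (sections 7.2.3 and 9.4). The check is therefore mainly a reading of the sections against each other.

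**1. Is the 30-day rule tied to umbrella entry?** Only the age criterion in section 7.2.1 is expressly fixed at study entry. The 30-day bullet has no anchor, and its first limb, current participation, can be read as a continuing condition. The two-person contrast needs the rule to be answered once, at umbrella entry, and no section says that.

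**2. Is a recheck ruled out?** Four places point the other way.
- Section 4.1: each sub-study is submitted separately with its own plan and consent form.
- Section 7.2: each sub-study specifies its own population within that of the umbrella.
- Section 7.2.7: subjects who meet all eligibility criteria may be randomised, and randomisation requirements are defined per sub-study.
- Section 10: consent is taken again for each sub-study, which provides an occasion for the check.

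In section 14 the sub-study list includes an open category of sub-study specific information, so leaving eligibility out of that short list does not show that it goes unchecked.

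**3. Would an earlier AI5763 sub-study trigger the 30-day rule?** The investigation in question is AI5763, and its sub-studies are parts of it. Successive sub-studies are expressly allowed. The natural reading is that another investigation means one outside AI5763.

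**4. Can Group 2 bypass the open-set criterion?** The alternative wording in section 7.2.1 leaves this possible. Section 7.1.1, however, admits implant recipients only if they meet the criteria of section 7.2, and refers to that section for recruitment. Recruitment under the Group 1 procedures can reasonably be taken to include the Group 1 criterion. Section 7.1 also cites Figure 5 for the enrolment scenarios of both groups. The figure is not visible here, so its content cannot be counted as missing.

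**5. What would be the size?** Time scale: the look-back is 30 days, and participation runs up to 5 × 365.25 = about 1,826 days. For dilution, let a fraction f of subjects be at floor with both maps and let d be the true mean difference in the others. Then

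expected mean difference = (1 − f) × d + f × 0 = (1 − f) × d.

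| f (assumed) | multiplier 1 − f |
|---|---|
| 5% | 0.95 |
| 10% | 0.90 |
| 20% | 0.80 |

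The documents give no value for f. They also do not say how many sub-studies a subject joins or how many subjects enter outside trials, so the number of wrongly admitted entries cannot be estimated.

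**The case for a change.** The strongest case for a change is that the word score applies across the umbrella. The Change History for version 6.0 calls it the consistent outcome in all fitting sub-studies, so a rule protecting it could sit in the umbrella plan. The contrast with the repeated medication check is fair, and section 7.2.7 sets no date for its eligibility condition. A clarifying sentence would cost little.

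The statistical direction is also right. Consider a simulation of a non-inferiority test based on the lower limit of the two-sided 95% paired-t interval, with the true difference in measurable subjects equal to the margin. With 4 of 20 subjects at floor, an assumed margin of 10 points and SD 10, false non-inferiority is about 13%, against a nominal 2.5%. With 2 of 20 at floor, margin 5 and SD 15, it is 3.6%.

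What stands is that the umbrella plan is silent on four details: a recheck, the date from which the 30 days run, the status of earlier AI5763 sub-studies, and the open-set criterion for Group 2. What does not stand is the step from silence to a failing rule. Every input to the error rates is assumed, and nothing in the plan suggests that a fifth of a fitting sub-study would be at floor on both maps. The umbrella states no hypothesis or margin, and in a superiority test the same dilution works against the new method. For recent outside exposure, no mechanism has been shown by which it would bias a comparison in which each subject is their own control.

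**Conclusion.** No change follows. The umbrella plan leaves a gap in detail, and it assigns populations, hypotheses and analyses to sub-study plans that are not among these documents. Investigators and analysts can be expected to fill the gap sensibly: confirm eligibility when sub-study consent is taken, count the 30 days from then, and treat only trials outside AI5763 as other investigations.

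Whether the open-set criterion should bind Group 2 subjects is a trade-off. An umbrella-wide requirement would protect word-score comparisons from floor effects, but would delay or exclude some newly implanted subjects. Leaving that choice to each sub-study, where the endpoint and any margin are set, is reasonable.

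The possible effect has a known form, shrinkage by the factor 1 − f, but no known size. The conclusion rests on the sub-study plans addressing entry, as sections 4.1 and 7.2 lead one to expect. A sub-study plan that claimed non-inferiority on word scores, admitted Group 2 subjects and was silent on open-set speech would deserve the question again, at that level.
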